2.9.1.3 Definition of Composite Endpoint

- Death due to any cause will be assessed through to 48 hours following PCI or hospital discharge, whichever comes first.
- Periprocedural myonecrosis will have occurred if there is at least one troponin (troponin I or troponin T) value of ≥ 3 times the upper limit of normal and at least 20% or greater than the baseline troponin value, per the troponin Local Laboratory, within 48 hours following PCI or hospital discharge, whichever comes first.
 - To be included in the primary composite endpoint analysis and in the secondary PPM endpoint analysis, a patient must have the pre-PCI troponin Local Laboratory measurement and at least one troponin Local Laboratory measurement within 48 hours following PCI or hospital discharge, whichever comes first.

- Patients without a pre-PCI troponin Local Laboratory measurement will not be included in the PPM endpoint analysis but will still be included in the intention to treat analysis and be analyzed for death and uTVR.
 - Patients without any troponin Local Laboratory measurements within 48 hours following PCI or hospital discharge, whichever comes first will not be included in the PPM endpoint analysis but will still be included in the intention to treat analysis and be analyzed for death, uTVR and major bleeding.
- Urgent Target Vessel Revascularization (uTVR) is either a PCI following the index PCI, or any CABG procedure performed after the index PCI on a non-selective basis in the target vessel because of recurrent myocardial ischemia. A revascularization procedure in the target vessel is considered urgent if it is due to one or more episodes of chest pain, presumed to be ischemic in origin and lasting at least 5 minutes, and results in either urgent repeat PCI or urgent coronary artery bypass surgery involving the target vessel. In the absence of pain, new ischemic ST-segment or T-wave changes, acute pulmonary edema, ventricular arrhythmias presumed to be ischemic in origin will constitute sufficient evidence of ischemia. The episode of ischemia leading to urgent repeat PCI must occur following completion of the index PCI and guidewire removal. For uTVR to count towards the primary composite endpoint, uTVR will have to be initiated during the course of the study (i.e., 48 hours following PCI or hospital discharge, whichever comes first).
- Major bleeding is defined using the criteria from the REPLACE-2 trial. Major bleeding is defined as follows:
- a. transfusion of ≥ 2 units whole blood or packed red blood cells, or
 - b. intracranial hemorrhage, or
 - c. retroperitoneal hemorrhage, or
 - d. decrease in Hgb more than 4 g/dL (or 12% of Hct) with no bleeding site identified despite attempts to determine, or
 - e. spontaneous or non-spontaneous blood loss associated with a Hgb drop > 3 g/dL (or 10% of Hct) with an overt site of hemorrhage.

The REPLACE-2 Major bleeding definition takes into account blood transfusions, so that hemoglobin and hematocrit values are adjusted by 1 g/dl or 3%, respectively, for each unit of blood transfused.

Therefore, the true change in hemoglobin or hematocrit if there has been an intervening transfusion between two blood measurements is calculated as follows:

- Δ Hemoglobin = [baseline Hgb - post-transfusion Hgb] + [number of transfused units];
- Δ Hematocrit = [baseline Hct - post-transfusion Hct] + [number of transfused units x 3].

2.9.2 Safety

Safety will be assessed with:

- Nature, severity, and study drug relationship of all bleeding events, specifically,
 - Bleeding events according to REPLACE-2 Major bleeding definition
 - Bleeding events according to TIMI Major bleeding definition
 - Bleeding events according to REPLACE-2 Minor bleeding definition
 - Bleeding events according to TIMI Minor bleeding definition
 - Bleeding events according to REPLACE-2 Plus Major bleeding definition
 - Bleeding events according to TIMI Plus Major bleeding definition
 - Sum of REPLACE-2 Major and Minor bleeding
 - Sum of REPLACE-2 Plus Major and Minor bleeding
 - Sum of TIMI Major and Minor bleeding
 - Sum of TIMI Plus Major and Minor bleeding
- Non-bleeding adverse events
- Change in lab parameters, specifically,
 - Thrombocytopenia (< 100,000 cells/ μ L)
 - Severe Thrombocytopenia (< 50,000 cells/ μ L)
 - Profound Thrombocytopenia (< 20,000 cells/ μ L)
- Length of hospital stay.

3 STATISTICAL METHODS

3.1 Statistical Handling Policy

3.1.1 Analysis Conventions

This section details general guidelines to be used for the statistical analyses. Deviations from these general policies may be given in the specific detailed sections of this statistical analysis plan. When this situation occurs, the rules set forth in the specific section take precedence over the general conventions. The following policies will be applied to all data presentations and analyses:

- Two-tailed tests will be performed for analyses that use statistical testing with a significance level of $\alpha = 0.05$. One-tailed tests will be performed for analyses with a significance level of $\alpha = 0.025$, if applicable.
- Summary descriptive statistics will consist of the number and percentage of responses in each category for discrete variables, and the mean, median, standard deviation (SD), minimum, maximum, and 95% confidence interval for continuous variables.
- All mean and median values will be formatted to one decimal place. Standard deviation values will be formatted to two decimal places.
- All percentages will be rounded to one decimal place. Where appropriate, the number and percentage of responses will be presented in the form XX (XX.X %), where the percentage is in the parentheses.
- For any analysis output, estimates and their corresponding standard deviations and/or standard errors will be reported up to the 3rd or 4th decimal place, per the default output of SAS.
- All p-values will be rounded to 4 decimal places (SAS format p-value). All p-values that round to 0.000 will be presented as '<0.001' and p-values that round to 1.000 will be presented as '>0.999'. Any p-value ≤ 0.05 will be considered statistically significant.
- All listings will be sorted for presentation in order of treatment group, site number, subject number, and date of procedure or event, when applicable.

- When necessary for analysis purposes, partial dates will be imputed (i.e., turned into complete dates) using the most conservative approach.
- Where appropriate, all analyses and summary tables will have the population sample size for each treatment group in the column heading.
- Tables will include titles with the corresponding analysis population and footnotes describing the analyses involved, and listings of covariates included in the analyses, where relevant.
- Version 20.0 (or higher) of MedDRA will be used for adverse event and pre-treatment conditions coding.
- Version 2015 (or later) of the World Health Organization (WHO) Drug Classifications will be used for the coding of medications.
- Version 9.4 (or later) of SAS® will be the statistical software package used to produce all summaries, listings, statistical analyses, and graphs.

3.2 Analysis Population

The Modified Intent-to-treat (mITT) Population is defined as all randomized patients who underwent PCI and received study drug.

The Per Protocol (PP) Population will consist of all randomized patients who completed the full course of the study without major protocol violations.

The Safety Population is defined as all randomized subjects who received any study treatment. All efficacy analyses will be performed on the modified intent-to-treat population (mITT) and on the per-protocol population (PP). Safety analyses will be performed on the safety population.

3.3 Subject Disposition and Discontinuations

Patient disposition will be summarized for the total enrolled population and by treatment group.

The following data will be presented:

- The number of patients who were screened, enrolled and randomized

- The number and proportion of patients in each analysis population
- The number and percentage of patients who completed the study
- The number and percentage of patients who discontinued prematurely from the study and the associated reasons.

3.4 Treatment Exposure and Dosing

Treatment exposure will be calculated in terms of number of hours exposed to treatment using SAS function 'INTCK' in the following formula, and presented by the descriptive statistics including mean, median, SD, minimum, maximum and 95% CI of the mean:

$$\text{Exposure (hours)} = \text{INTCK ("Hour", Start of Dosing, End of Dosing)}$$

In addition, the cumulative dosing medication used will be calculated for each patient by computing the sum of study drug of tirofiban or eptifibatide administered pre and post-PCI.

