Patients assigned to short tirofiban with renal insufficiency (creatinine clearance ≤ 60 mL/min) will receive a 25 $\mu\text{g}/\text{kg}$ bolus followed by a 0.075 $\mu\text{g}/\text{kg}/\text{min}$ maintenance infusion for the duration of the PCI procedure plus a minimum of one hour and up to a maximum of two hours post-PCI.

Patients assigned to eptifibatide will receive a 180 $\mu\text{g}/\text{kg}$ bolus followed by a 2.0 $\mu\text{g}/\text{kg}/\text{min}$ infusion for 18 hours post-PCI (minimum 12 hours mandated), with a second 180 $\mu\text{g}/\text{kg}$ bolus 10 min after the first.

Patients assigned to eptifibatide with renal insufficiency (creatinine clearance < 50 mL/min) will receive a 180 $\mu\text{g}/\text{kg}$ bolus followed by a 1.0 $\mu\text{g}/\text{kg}/\text{min}$ infusion for 18 hours post-PCI (minimum 12 hours mandated), with a second 180 $\mu\text{g}/\text{kg}$ bolus 10 min after the first.

Patients assigned to long tirofiban received a 25 $\mu\text{g}/\text{kg}$ bolus administered by I.V. push followed by a 0.15 $\mu\text{g}/\text{kg}/\text{min}$ infusion for 12-18 hours post-PCI.

Patients assigned to long tirofiban with renal insufficiency (creatinine clearance ≤ 60 mL/min) received a 25 $\mu\text{g}/\text{kg}$ bolus followed by a 0.075 $\mu\text{g}/\text{kg}/\text{min}$ maintenance infusion for 12-18 hours post-PCI.

The study drug boluses of tirofiban or eptifibatide will be administered intravenously by volume according to patient weight (see Appendix 3 for dosing tables). The bolus volume and infusion rate increases with increasing patient weight, but is capped at the patient weight of 153 kg and 121 kg for tirofiban and eptifibatide, respectively. Therefore, any patient randomized to tirofiban weighing over 153 kg will receive the same bolus volume and infusion rate as a patient randomized to tirofiban weighting 153 kg. Similarly, any patient randomized to eptifibatide weighing over 121 kg will receive the same bolus volume and infusion rate as a patient randomized to eptifibatide weighting 121 kg. Administration of the bolus will begin prior to the initiation of the PCI procedure. Initiation of the PCI procedure is defined as advancement of the guidewire out of the guiding catheter.

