5.2.5 Following the Procedure

Short tirofiban will be infused for the duration of the procedure plus a minimum of one hour and up to a maximum of two hours post-PCI. For example, if the procedure takes 25 minutes (i.e. 25 minutes from the time of advancement of the guidewire out of the guiding catheter to final removal of the guiding catheter) then tirofiban will be infused for a total of 25 minutes plus a minimum of one hour (for a total infusion time of 85 minutes) and up to a maximum of two hours (for a total infusion time of 145 minutes). For another example, if the PCI procedure takes 55 minutes, then tirofiban will be infused for a total of 55 minutes plus a minimum of one hour (for a total infusion time of 115 minutes) and up to a maximum of two hours (for a total infusion time of 175 minutes).

Eptifibatide will be infused for a total of 18 hours following PCI (minimum 12 hours mandated).

Long tirofiban was infused for a total of 18 hours following PCI (minimum 12 hours mandated).

During study drug administration and following discontinuation of study drug, the patient will be observed for signs of bleeding. Blood pressure and heart rate will be monitored according to the institution's standard procedures.

For the definition of procedure duration, final removal of the guiding catheter will define procedure completion.

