Modified Intent-to-Treat Population (mITT) ¹ , n (%) *				
Per-Protocol Population (PP) ² , n (%) *				
Safety Population I ³ , n (%)				
Completed the study, n (%) *				
Yes				
No				
If no, reason for non-completion of the study, n (%) †				
Non-compliance with study protocol				
Adverse event				
Death				
Withdrawal of consent				
Treating physician decision to withdraw subject				
Other reason				

¹ Defined as all randomized patients who underwent PCI and received study drug.

² Defined as all randomized patients who completed the full course of the study without major protocol violations.

³ Defined as all randomized patients who received any study treatment.

* Percentages based on the total number of mITT patients in each treatment group.

† Percentages based on the total number of mITT patients who had a premature study discontinuation.

Table 2a. Treatment Exposure and Dosing by Treatment Group – mITT Population without renal insufficiency¹

Parameter	Treatment Group		
	Short Tirofiban (N=)	Eptifibatide (N=)	Long Tirofiban (N=)
Number of hours exposed to treatment drug			
Available n			
Mean ± SD			
95% CI for Mean			
Median (IQR)			
Min - Max			
Cumulative treatment drug received (µg)			
Available n			
Mean ± SD			
95% CI for Mean			
Median (IQR)			
Min - Max			

¹ Creatinine clearance >60 mL/min

Note: This table will also be repeated for Per-Protocol Population.

Table 2b. Treatment Exposure and Dosing by Treatment Group – mITT Population with renal insufficiency¹

Parameter	Treatment Group		
	Short Tirofiban (N=)	Eptifibatide (N=)	Long Tirofiban (N=)
Number of hours exposed to treatment drug			
Available n			
Mean ± SD			
95% CI for Mean			
Median (IQR)			
Min - Max			
Cumulative treatment drug received (µg)			
Available n			
Mean ± SD			
95% CI for Mean			
Median (IQR)			
Min - Max			

¹ Creatinine clearance ≤60 mL/min

Note: This table will also be repeated for Per-Protocol Population.

Table 3. Patient Demographics and Baseline Characteristics by Treatment Group – mITT Population

Parameter	Treatment Group		
	Short Tirofiban (N=)	Short Tirofiban (N=)	Short Tirofiban (N=)
Age (years)			
Available n			
Mean ± SD			
95% CI for Mean			
Median (IQR)			
Min - Max			
Gender, n (%)			
Female			
Male			
Ethnicity, n (%)			
Latino			
Non-Latino			
Race, n (%)			
White			
Black or African American			
Asian			
Native Hawaiian or other Pacific Islander			
American Indian or Alaska Native			
Other			

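### SAP 3.4 counts clock-hour boundaries instead of elapsed time, so the exposure-hours statistics in Tables 2a and 2b are wrong; the same tables mix infusion rates

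*SAP*

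**What the plan says.** SAP 3.4 defines exposure as the "number of hours exposed to treatment using SAS function" INTCK, called with three arguments: the Hour interval, the start of dosing and the end of dosing. There is no method argument and no correction for part hours. The result is to be "presented by the descriptive statistics including mean, median, SD, minimum, maximum and 95% CI of the mean". SAP 3.1.1 fixes the software: "Version 9.4 (or later) of SAS® will be the statistical software package used". No other SAP section replaces the formula. It feeds the hours-exposed rows of mock Tables 2a and 2b, which are repeated for the per-protocol population.

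The protocol works in minutes. Section 5.2.5 takes a 25-minute procedure plus the one-hour minimum, "for a total infusion time of 85 minutes", and also gives 145, 115 and 175 minutes. Section 1.4.4 gives 165 minutes. The other two arms run for 18 hours after PCI, with a 12-hour minimum.

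On renal function, Table 2a is footnoted "Creatinine clearance >60 mL/min" and Table 2b takes the remainder, for all three arms. Protocol 5.2.3 sets a different limit for one arm: "Patients assigned to eptifibatide with renal insufficiency", meaning clearance below 50 mL/min, receive half the usual infusion rate. Appendix 3 records that the tirofiban renal threshold changed after 159 patients and the reduced rate after 167.

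**The concern.** Infusion duration is what separates short tirofiban from the other two arms, and Tables 2a and 2b are where the report will show it. A whole-hour count that depends on the minute at which dosing began is a poor description of infusions lasting roughly one and a half to three hours. A reader of those tables would see a spread and a range that partly reflect the clock and not the treatment.

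The renal split raises a second question in the same tables. If one column holds patients on different infusion rates, its cumulative-dose summary describes neither group.

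**Working it through.** **Inputs.** The durations come from Protocol 5.2.5 and 1.4.4, and the formula from SAP 3.4. How INTCK behaves is general knowledge of the named function and is not stated in the documents.

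**Reproducing the protocol's durations.** Procedure plus post-PCI minutes: 25 + 60 = 85; 25 + 120 = 145; 55 + 60 = 115; 55 + 120 = 175; 45 + 120 = 165. All five agree.

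**What the formula returns.** With times in minutes, the default count is floor(end/60) − floor(start/60). Over all 60 start minutes:

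| True minutes | Elapsed hours | Recorded hours (start minutes) | Largest error |
|---|---|---|---|
| 85 | 1.417 | 1 (35/60) or 2 (25/60) | 0.583 h, 41% |
| 115 | 1.917 | 1 (5/60) or 2 (55/60) | 0.917 h, 48% |
| 145 | 2.417 | 2 (35/60) or 3 (25/60) | 0.583 h, 24% |
| 165 | 2.750 | 2 (15/60) or 3 (45/60) | 0.750 h, 27% |
| 175 | 2.917 | 2 (5/60) or 3 (55/60) | 0.917 h, 31% |
| 765 (45 min + 12 h) | 12.750 | 12 (15/60) or 13 (45/60) | 0.750 h, 6% |
| 1125 (45 min + 18 h) | 18.750 | 18 (15/60) or 19 (45/60) | 0.750 h, 4% |

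All five short-arm examples can be recorded as 2 h. An infusion of 12 h 55 min recorded as 12 h is out by 0.917/12.917 = 7.1%. Because the error is always under 1 h, it is below 1/12 = 8.3% for any infusion of 12 h or more.

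**Mean.** With start minutes evenly spread, the 85-minute case averages (35 × 1 + 25 × 2)/60 = 1.417 h, the true value. If recorded starts cluster, the mean moves: 165 minutes begun on the hour is always counted as 2 h.

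**Spread.** One million patients per duration pattern were simulated, assuming procedures of 25–55 min, post-PCI infusion of 60–120 min (short) or 720–1080 min (long), and start times, all uniform:

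| Duration pattern | True mean, SD (h) | Recorded mean, SD (h) | True median, range (h) | Recorded median, range (h) | Mean absolute error |
|---|---|---|---|---|---|
| Short tirofiban | 2.17, 0.33 | 2.17, 0.53 | 2.17, 1.42–2.92 | 2, 1–3 | 0.33 h (15% of mean) |
| 12–18 h arms | 15.67, 1.74 | 15.67, 1.79 | 15.67, 12.42–18.92 | 16, 12–19 | 0.33 h (2% of mean) |

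In the short pattern 26% of patients are out by 30 minutes or more. A hand check agrees. If f is the part-hour of a duration, counting boundaries adds variance f(1 − f), which averages 1/2 − 1/3 = 1/6 when f is uniform. Then √(0.329² + 1/6) ≈ 0.52 and √(1.744² + 1/6) ≈ 1.79.

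**Renal split.** Eptifibatide patients at 50–60 mL/min receive the full rate but fall in Table 2b with half-rate patients. For the 90 kg patient used in Protocol 1.4.4, over 18 h and ignoring procedure time, the two boluses give 2 × 180 × 90 = 32,400 µg. The infusion gives 2.0 × 90 × 1080 = 194,400 µg at the full rate or 97,200 µg at half rate. The totals are 226,800 and 129,600 µg, a ratio of 1.75. The tirofiban columns are mixed too. Before the change after 159 patients the reduced-rate threshold was 30 mL/min, and the reduced rate itself later went from 0.10 to 0.075 µg/kg/min.

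**The case against.** The strongest reply is that this is a descriptive row. The comparisons in SAP 3.10.1 to 3.10.3 do not use it, cumulative dose is a separate sum of drug administered, the arm mean is right if start minutes are evenly spread, and the absolute error is no larger in the short arm than elsewhere. All of that stands, and it limits how serious the point is. It does not rescue the SD, confidence interval, median, minimum and maximum, which SAP 3.4 undertakes to report.

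A common 60 mL/min cut can also be defended, because it keeps the columns comparable in renal function. That holds for describing patients, but not for summarising dose received.

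Three stronger readings are tempting, and the documents do not support them:

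- **That this variable checks the 1–2 hour post-PCI rule.** No section gives it that role. It runs from start of dosing and so includes the procedure: an exact 145 minutes could be 25 + 120 or 55 + 90. A simple share of short-arm patients inside the window would also misclassify those with a thrombotic complication, whose infusion Protocol 5.1 and 5.2.4 extend to at least 12 hours.
- **That the error carries into the total-infusion-time covariate.** SAP 3.10.4 lists it without a derivation. Its absence from Table 13, which covers covariates not summarised elsewhere, makes reuse plausible but does not establish it.
- **That splitting Tables 2a and 2b at each arm's own threshold cures the mixing.** There was no single tirofiban threshold or reduced rate across the trial.

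**Conclusion.** The point holds as a reporting error. Followed as written, SAP 3.4 records clock-boundary counts in place of elapsed hours. Individual errors are under 1 h in every arm. They are large relative to the short-tirofiban duration (up to 48% in the protocol's own examples) and small for infusions of 12 h or more (below 8.3%). Under the simulation's assumptions the short-arm SD is about 60% too large (0.525/0.329 = 1.60), and the confidence interval for the mean widens in proportion.

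The conclusion assumes default INTCK behaviour and that start and end of dosing are datetimes. With time-only values, an infusion from 16:00 to 10:45 the next day would return 10 − 16 = −6. The simulated SD leaves out short-arm patients whose infusion is extended for a thrombotic complication. Including them would raise the true SD and reduce the relative inflation.

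The trial's non-inferiority conclusions are not touched. The total-infusion-time covariate is affected only if it reuses the formula. The renal mismatch is real, but its effect on the tables cannot be sized because the documents do not give the number of patients in the affected clearance bands.

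**What to change.** In SAP 3.4, define exposure in hours as (end datetime − start datetime)/3600 and report it to one or two decimals. The protocol's 85, 145 and 165 minutes then appear as 1.417, 2.417 and 2.75 h before rounding. Adding the continuous method to INTCK is not enough, because it still truncates to whole hours (1, 2 and 2 for those three). State in SAP 3.10.4 that total infusion time uses the same derivation.

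Present Tables 2a and 2b by infusion rate actually received, and footnote the rates. This is a change to how the data are reported, not to any dose.

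The cost is a line or two of SAP text and code, a change to the table grouping and a footnote. The hours calculation needs only the start and end times the present formula already uses.

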3.5 Subject Demographics and Baseline Characteristics

Descriptive statistics will be presented for all patient demographic and characteristics data including age, gender, ethnicity and race. Age will be calculated as follows: Age = Largest Integer \leq [(Visit 1 Date – Date of Birth + 1)/365.25; or as per the SAS function Age=YRDIF (date of birth, baseline date, 'ACTUAL').

3.6 Medical History

Medical conditions will be coded using the Medical Dictionary for Regulatory Activities (MedDRA) and the number and percentage of subjects with medical history will be reported by System Organ Class (SOC) and Preferred Term (PT).

